11. MEASUREMENT OF EFFECT

11.1 Antitumor Effect – Solid Tumors

For the purposes of this study, participants should be re-evaluated for response every 12 weeks (\pm 7 days). In addition to a baseline scan, confirmatory scans should also be obtained 12 (not less than 6) weeks following initial documentation of progressive disease.

Response and progression will be evaluated in this study using the new international criteria proposed by the Response Evaluation Criteria in Solid Tumors (RECIST) guideline (version $1.1)^{52}$ and PCWG2²³.

11.1.1 Definitions

Eligibility requires lack of measurable disease by RECIST v1.1. As such, all baseline lesions would be considered non-target.

Evaluable Non-Target Disease Response. Participants who have lesions present at baseline that are evaluable but do not meet the definitions of measurable disease, have received at least one cycle of therapy, and have had their disease reevaluated will be considered evaluable for non-target disease. The response assessment is based on the presence, absence, or unequivocal progression of the lesions.

11.1.2 Disease Parameters

Measurable disease:

Note: Patients are not eligible if they have measurable disease for this study.

Measurable lesions are defined as those that can be accurately measured in at least one dimension (longest diameter to be recorded) as ≥ 20 mm by chest x-ray or ≥ 10 mm with CT scan, MRI, or calipers by clinical exam. All tumor measurements must be recorded in millimeters (or decimal fractions of centimeters).

Note: Tumor lesions that are situated in a previously irradiated area can still be considered measurable if they have grown since the last time of radiation on at least 2 subsequent scans.

Malignant lymph nodes: To be considered pathologically enlarged and measurable, a lymph node must be ≥ 15 mm in short axis when assessed by CT scan (CT scan slice thickness recommended to be no greater than 5 mm). At baseline and in follow-up, only the short axis will be measured and followed.

Non-measurable disease: All other lesions (or sites of disease), including small lesions (longest diameter <10 mm or pathological lymph nodes with \geq 10 to <15 mm short axis), are considered non-measurable disease. Bone lesions, leptomeningeal disease, ascites, pleural/pericardial effusions, lymphangitis cutis/pulmonitis, inflammatory breast disease, abdominal masses (not followed by CT or MRI), and cystic lesions are all considered non-measurable.

Note: Cystic lesions that meet the criteria for radiographically defined simple cysts should not be considered as malignant lesions (neither measurable nor non-measurable) since they are, by definition, simple cysts.

'Cystic lesions' thought to represent cystic metastases can be considered as measurable lesions, if they meet the definition of measurability described above. However, if non-cystic lesions are present in the same participant, these are preferred for selection as target lesions.

Non-target lesions. All bone lesions should be identified as **non-target lesions** and should also be recorded at baseline. Measurements of these lesions are not required, but the presence, absence, or in rare cases unequivocal progression of each should be noted throughout follow up.

11.1.3 Methods for Evaluation of Disease

Imaging studies will be reviewed by independent radiologists at the Tumor Imaging Metrics Core at DFCI. Ultimately, all scans will undergo central review at DFCI for final response analysis. However, for eligibility and ongoing response assessment while on study therapy, UCSF review will be per investigator assessment.

All measurements should be taken and recorded in metric notation using a ruler, calipers, or a digital measurement tool. All baseline evaluations should be performed as closely as possible to the beginning of treatment and not more than 42 days before the beginning of the treatment.

The same method of assessment and the same technique should be used to characterize each identified and reported lesion at baseline and during follow-up. Imaging-based evaluation is preferred to evaluation by clinical examination unless the lesion(s) being followed cannot be imaged but are assessable by clinical exam.

Conventional CT and MRI. This guideline has defined measurability of lesions on CT scan based on the assumption that CT thickness is 5mm or less. If CT scans have slice thickness greater than 5 mm, the minimum size of a measurable lesion should be twice the slice thickness. MRI is also acceptable in certain situations (*e.g.* for body scans).

Use of MRI remains a complex issue. MRI has excellent contrast, spatial, and temporal resolution; however, there are many image acquisition variables involved in MRI, which greatly impact image quality, lesion conspicuity, and measurement. Furthermore, the availability of MRI is variable globally. As with CT, if an MRI is performed, the technical specifications of the scanning sequences used should be optimized for the evaluation of the type and site of disease. Furthermore, as with CT, the modality used at follow-up should be the same as was used at baseline and the lesions should be measured/assessed on the same pulse sequence. It is beyond the scope of the RECIST guidelines to prescribe specific MRI pulse sequence parameters for all scanners, body parts, and diseases. Ideally, the same type of scanner should be used and the image acquisition protocol should be followed as closely as possible to prior scans. Body scans should be performed with breath-hold scanning techniques, if possible.

Tumor markers. Tumor markers alone cannot be used to assess response. If markers are initially above the upper normal limit, they must normalize for a participant to be considered in complete clinical response.

Cytology, Histology. These techniques can be used to differentiate between partial responses (PR) and complete responses (CR) in rare cases.

The cytological confirmation of the neoplastic origin of any effusion that appears or worsens during treatment when the measurable tumor has met criteria for response or stable disease is mandatory to differentiate between response or stable disease (an effusion may be a side effect of the treatment) and progressive disease.

11.1.4 Evaluation of Bone Lesions

Existing bone metastases will be the only lesions in some patients. Because bone lesions are notoriously difficult to follow, 'progression' in non-target lesions is defined as the appearance of ≥2 new lesions, and, for the first reassessment only, a confirmatory scan performed 6 or more weeks later is required that shows a minimum of 2 or more additional new lesions (PCWG2 criteria).

Complete Response (CR): Disappearance of all non-target lesions and normalization of PSA. All lymph nodes must be non-pathological in size (<10 mm short axis).

Non-CR/Non-PD: Persistence of one or more non-target lesion(s) and/or maintenance of tumor marker level above the normal limits.

Progressive Disease (PD): Appearance of one or more new lesions and/or *unequivocal progression* of existing non-target lesions. It must be representative of overall disease status change, not a single lesion increase.

Although a clear progression of "non-target" lesions only is exceptional, the opinion of the treating physician should prevail in such circumstances, and the progression status should be confirmed at a later time by the review panel (or Principal Investigator).

Definitions of Progression:

1. Bone Progression:

Appearance of 2 or more new lesions on bone scan, and, for the first reassessment only, a confirmatory scan performed 6 or more weeks later that shows a minimum of 2 or more additional new lesions. The date of progression is the date of the first scan that shows the change.

2. Soft Tissue Progression:

Soft tissue disease progression by modified RECIST v1.1 with additional requirement that progression at first assessment be confirmed by a second scan 6 or more weeks later. Note that for some treatments, a lesion may increase in size before it decreases.

3. Symptomatic Progression:

Symptomatic progression is defined as evidence of unequivocal symptomatic or clinical progression defined by at least 1 of the following:

- A marked escalation in cancer-related pain that is assessed by the Investigator to indicate the need for other systemic therapy or palliative radiotherapy. Ignore early changes (≤ 12 weeks) in pain or health-related quality of life in absence of compelling evidence of disease progression. Confirm progression of pain or health-related quality of life ≥ 3 weeks later
- An immediate need for initiation of new anticancer treatment or surgical intervention for complications due to tumor progression. Palliative radiation is allowed while on therapy to combat symptomatic/clinical progression and does not require that the patient discontinue study therapy unless treating investigator does not believe they are deriving any clinical benefit.
- A marked deterioration in ECOG performance status to Grade 3 or higher, or
- It is felt to be in the best interest of the patient to come off study due to clinical progression

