11.1.5 Evaluation of New Lesions

The finding of a new lesion should be unequivocal (i.e. not due to difference in scanning technique, imaging modality, or findings thought to represent something other than tumor (for example, some 'new' bone lesions may be simply healing or flare of pre-existing lesions). However, a lesion identified on a follow-up scan in an anatomical location that was not scanned at baseline is considered new and will indicate PD. If a new lesion is equivocal (because of small size etc.), follow-up evaluation will clarify if it truly represents new disease and if PD is confirmed, progression should be declared using the date of the initial scan on which the lesion was discovered.

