11.1.6 Evaluation of Best Overall Response

The best overall response is the best response recorded from the start of the treatment until disease progression/recurrence (taking as reference for progressive disease the smallest measurements recorded since the treatment started). The patient's best response assignment will depend on the achievement of both measurement and confirmation criteria.

For Participants with Non-Measurable Disease (*i.e.*, Non-Target Disease): all patients in this study will have non-measurable bone only disease

Non-Target Lesions	New Lesions	Overall Response				
CR	No	CR				
Non-CR/non-PD	No	Non-CR/non-PD*				
Not all evaluated	No	not evaluated				
Unequivocal PD	Yes or No	PD				
Any	Yes	PD				
* 'Non-CR/non-PD' is preferred over 'stable disease' for non-target disease since SD is increasingly used as an endpoint for assessment of efficacy in some trials so to assign this category when no lesions can be measured is not advised						

Table 16: Evaluation of Overall Response

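### A single new bone lesion both is and is not a progression event for the secondary PFS endpoint, because Section 11.1 carries a one-lesion and a two-lesion rule and never says which governs bone

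*Combined protocol and SAP*

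**What the plan says.** Two rules for new lesions stand in the current text.

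**Two or more lesions.** Section 11.1.4 opens with a rule for patients whose disease is hard to follow in bone: "progression' in non-target lesions is defined as the appearance of ≥2 new lesions". It labels this rule as PCWG2. Definition 1 under the definitions of progression repeats it: "Appearance of 2 or more new lesions on bone scan, and, for the first reassessment only, a confirmatory scan performed 6 or more weeks later" has to show at least two further new lesions.

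**One lesion.** Between those two statements, the response categories of 11.1.4 give progressive disease as "Appearance of one or more new lesions" and/or unequivocal progression of existing non-target lesions. This line makes no exception for bone and asks for no confirmation. In Section 11.1.6, "Table 16: Evaluation of Overall Response" has a row in which any non-target status plus a new lesion gives PD. The table is introduced with the statement that "all patients in this study will have non-measurable bone only disease". Section 11.1.5 adds that a lesion found in a region not imaged at baseline "is considered new and will indicate PD".

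**The endpoint.** Section 13.1 defines secondary PFS by definitive progression under RECIST 1.1 and PCWG2, as does the opening of 11.1. Neither assigns bone to one of them. For the genomic analyses, Section 13.1 gives a separate PFS definition, which requires two or more new bone lesions confirmed at least 6 weeks later.

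**The concern.** Section 11.1.1 makes every baseline lesion non-target, so the non-target rules reach every patient, and new bone lesions are a main route to progression in this population. If the text allows two answers for one new bone lesion, the PFS event and its date are not defined by the plan for that patient. The choice could then be made after data are seen, in an open-label trial where ongoing assessment at one of the two sites is by the investigator. Central review does not settle it, because the central reader works from the same two rules. Time to progression (11.1.8) and best overall response (11.1.6) rest on the same wording. So do the treatment decisions in Section 5.4 that turn on meeting the protocol's progression criteria.

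**Working it through.** **Step 1: one test case.** Take a patient with one unequivocal new bone lesion and no other change.

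| Provision | Result |
|---|---|
| 11.1.4, opening sentence | not progression |
| 11.1.4, PD category | PD |
| 11.1.4, definition 1 (bone) | not progression |
| 11.1.5, if the region was not imaged at baseline | PD |
| 11.1.6, Table 16, any status with a new lesion | PD |
| 13.1, genomic PFS | not an event |
| 13.1, secondary PFS | undetermined: cites both criteria |

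**Step 2: is there a saving clause?** The PD line is followed by "It must be representative of overall disease status change, not a single lesion increase". That sentence concerns growth of a lesion already present and does not settle the status of one new lesion. No provision says that definition 1 overrides the PD category or Table 16.

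**Step 3: illustration of size.** The documents give no rate of new bone lesions. Assume that they arrive singly as a Poisson process, with a median of 6 months to the second lesion.

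- Rate: the median of a gamma distribution with shape 2 is 1.678, so λ = 1.678/6 = 0.280 per month. Median to the first lesion = ln 2/0.280 = 2.5 months.
- First scan: 12 weeks = 84/30.44 = 2.76 months, so λt = 0.772.
- One-lesion rule: 1 − exp(−0.772) = 0.54.
- Two-lesion rule before confirmation: 1 − exp(−0.772) × (1 + 0.772) = 0.18.
- Two-lesion rule with the stated confirmation (two or more additional lesions on the later scan):
  - 6 weeks later, λt = 0.386 and the chance of two more is 0.058, so 0.181 × 0.058 = 0.010.
  - 12 weeks later, the chance is 0.181, so 0.181 × 0.181 = 0.033.

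The contrast at the first scan is therefore 54% against 18% unconfirmed, or about 1% to 3% confirmed.

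**Step 4: medians on the scan grid.** With 12-week scans, the one-lesion median falls at the first scan (2.8 months). The unconfirmed two-lesion median falls at the third (8.3 months), because 45.7% have two lesions by the second scan at 5.5 months. If the assumed median to the second lesion is 5.5 months instead of 6, 50.2% have two lesions by that scan and the median drops to 5.5 months. Without the grid, the contrast is 2.5 against 6.0 months.

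**The case against.** The best defence is that the specific rule prevails over the general. The PD line sits in a block of response categories that also covers lymph nodes and PSA, so despite its heading the block can be read as a general non-target classification. Bone and soft tissue are then separated under the definitions of progression. The two-lesion rule for bone appears in the opening sentence of 11.1.4, in definition 1, in Section 5.4 and in the genomic PFS. This is a natural reading, and probably the intended one. It does not remove the conflict: nothing states it, and Table 16 is itself addressed to bone-only disease.

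Several limits do stand.

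- A reader might infer that the DNA-repair analyses are compromised. They are not: their PFS definition in 13.1 is explicitly two-lesion and confirmed.
- A reader might infer that the one-lesion rule removes all protection against bone flare. Section 11.1.5 requires any new lesion to be unequivocal, names flare, and sends equivocal lesions to follow-up. What is lost is the lesion count and the mandatory confirmation.
- A reader might take 2.8 against 8.3 months as the effect on PFS. The lesion rate is assumed, the 8.3 is partly produced by the scan grid, and death, soft-tissue and symptomatic progression are left out. Including these other events would narrow the gap.
- The bone-only description comes from 11.1.6. Section 11.1.4 says bone is the only site in some patients, and the exclusion criteria admit certain stable nodes, lung nodules and small soft-tissue lesions.

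**Conclusion.** The inconsistency is real and lies in the current text. For the secondary PFS endpoint and time to progression, a single new bone lesion is an event under the PD category of 11.1.4 and Table 16, and no event under the opening sentence and definition 1 of 11.1.4.

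Severity is moderate. PFS is a secondary endpoint, investigated on a preliminary basis and summarised by Kaplan-Meier within each arm, with no between-arm test planned in Section 13.8. A reader might infer that the trial's main comparison or its 45 patients are in question. The documents do not support that, because the primary endpoint and its power calculation rest on biopsies.

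The finding itself rests only on the text. The first-scan percentages show that the choice of rule can matter a good deal at week 12, but they depend on the assumed lesion rate and are not estimates for this trial.

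**What to change.** For the PFS and time-to-progression endpoints only:

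1. Limit three provisions to non-bone (soft-tissue or visceral) lesions: the one-lesion PD line in 11.1.4, the row of Table 16 that turns any new lesion into PD, and the sentence in 11.1.5 on regions not imaged at baseline.
2. State in 11.1.8 and 13.1 that definition 1 of 11.1.4 governs bone.
3. Align the confirmation rule of definition 1 with the genomic PFS in 13.1. Definition 1 requires confirmation at the first reassessment only and asks for at least two additional lesions. The genomic definition asks for a repeat scan at least 6 weeks later, without either condition.

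Where Section 5.4 relies on the same progression wording for treatment decisions, those passages must also be reconciled. This review does not say which clinical rule should apply.

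The cost is a wording amendment, with no added scans or patients. It should be settled before progression dates are adjudicated for analysis.

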11.1.5 Evaluation of New Lesions

The finding of a new lesion should be unequivocal (i.e. not due to difference in scanning technique, imaging modality, or findings thought to represent something other than tumor (for example, some 'new' bone lesions may be simply healing or flare of pre-existing lesions). However, a lesion identified on a follow-up scan in an anatomical location that was not scanned at baseline is considered new and will indicate PD. If a new lesion is equivocal (because of small size etc.), follow-up evaluation will clarify if it truly represents new disease and if PD is confirmed, progression should be declared using the date of the initial scan on which the lesion was discovered.

11.1.6 Evaluation of Best Overall Response

The best overall response is the best response recorded from the start of the treatment until disease progression/recurrence (taking as reference for progressive disease the smallest measurements recorded since the treatment started). The patient's best response assignment will depend on the achievement of both measurement and confirmation criteria.

For Participants with Non-Measurable Disease (*i.e.*, Non-Target Disease): all patients in this study will have non-measurable bone only disease

Non-Target Lesions	New Lesions	Overall Response				
CR	No	CR				
Non-CR/non-PD	No	Non-CR/non-PD*				
Not all evaluated	No	not evaluated				
Unequivocal PD	Yes or No	PD				
Any	Yes	PD				
* 'Non-CR/non-PD' is preferred over 'stable disease' for non-target disease since SD is increasingly used as an endpoint for assessment of efficacy in some trials so to assign this category when no lesions can be measured is not advised						

Table 16: Evaluation of Overall Response

11.1.7 Duration of Response

Duration of overall response: The duration of overall response is measured from the time measurement criteria are met for CR or PR (whichever is first recorded) until the first date that recurrent or progressive disease is objectively documented (taking as reference for progressive disease the smallest measurements recorded since the treatment started, or death due to any cause. Participants without events reported are censored at the last disease evaluation).

Duration of overall complete response: The duration of overall CR is measured from the time measurement criteria are first met for CR until the first date that progressive disease is objectively documented, or death due to any cause. Participants without events reported are censored at the last disease evaluation.

Duration of stable disease: Stable disease is measured from the start of the treatment until the criteria for progression are met, taking as reference the smallest measurements recorded since the treatment started, including the baseline measurements.

11.1.8 Evaluation of Time to Event Endpoints

Progression-Free Survival: Progression-Free Survival (PFS) is defined as the time from randomization (or registration) to the earlier of progression or death due to

any cause. Participants alive without disease progression are censored at date of last disease evaluation.

Time to Progression: Time to Progression (TTP) is defined as the time from randomization (or registration) to progression, or censored at date of last disease evaluation for those without progression reported.

Overall Survival: Overall Survival (OS) is defined as the time from randomization (or registration) to death due to any cause, or censored at date last known alive.

11.1.9 Methods for Evaluation of Changes in PSA

Biochemical Response:53

The laboratory will utilize a consistent method to check serum PSA at baseline, every other cycle while on treatment, and at study termination.

PSA decline \geq 50% from baseline to 12 weeks of therapy and which has been confirmed with a second PSA at \geq 3 weeks later.

Percent change in serum PSA:²³

The percent change (rise or fall) from baseline at 12 weeks, and separately, the maximal change (rise or fall) at any time will be recorded using a waterfall plot.

PSA Progression:

PSA progression is defined as $\geq 25\%$ increase and ≥ 2 ng/mL increase above the nadir or baseline value for patients who had a PSA decrease on treatment which is confirmed by a second value 3 or more weeks later.

For patients without a decrease on treatment, PSA progression is defined as $\geq 25\%$ and a $\geq 2 \text{ ng/mL}$ after 12 weeks.

PSA progression must be confirmed at the next study visit 4 weeks later.

PSA progression alone will not be considered diagnostic of disease progression, and will not be used as a reason to discontinue study treatment.

12. DATA REPORTING / REGULATORY REQUIREMENTS

Adverse event lists, guidelines, and instructions for AE reporting can be found in Section 7.0 (Adverse Events: List and Reporting Requirements).

